2. INTRODUCTION

2.1 Drug variability

The response of one individual to its treatment is the result of its efficacy at the therapeutic target (pharmacodynamics, PD) and its disposition in the body (pharmacokinetics, PK).¹

Pharmacokinetics is the result of different stages: absorption of the drug into systemic circulation, tissue distribution, metabolism and elimination. Metabolism and elimination are the main PK causes of drug variability. While elimination occurs primarily in the faeces or by renal route, metabolism is mainly mediated by hepatocytes in the liver. Hepatocytes contain various enzymes whose main function is the transformation of a lipophilic drug into a hydrophilic metabolite with high excretion capability.²

2.2 Cytochromes P450

Cytochromes P450 (CYP450) constitute the main enzyme family responsible for oxidative metabolism (phase I) of major drugs and xenobiotics.³ In human, 57 functional genes have been identified. These are grouped in 18 families and 44 sub-families.⁴ Most of them have endogenous functions such as biosynthesis of steroid hormones, prostaglandins and bile acids.⁵ Drugs are metabolized by only 12 CYP isoenzymes, which belong to families 1-3. The most important isoenzymes in drug metabolism are CYP3A4/5 (which metabolizes 30.2% of drugs), CYP2D6 (20%), CYP2C9 (12.8%), CYP1A2 (8.9%), CYP2B6 (7.2%), and CYP2C19 (6.8%).⁶

2.3 Presentation and variability of CYP2C19

Despite its relatively low abundance in the liver (<4%), CYP2C19 metabolizes a large number of commonly used drugs such as proton pump inhibitors (e.g. omeprazole), antidepressants (e.g. citalopram), benzodiazepines (e.g. diazepam), the antiplatelet prodrug clopidogrel and mephénytoin.⁷ A huge variability in the activity of CYP2C19 has been observed in the general population. Indeed, the AUC of omeprazole, a known specific substrate of CYP2C19, is four to twelve times higher in poor metabolizers (PM) than in normal metabolizers (NM).⁸⁻¹¹

Five main phenotypes of CYP2C19 activity have been described to date. Normal metabolizers (NM) represent most of the population. Some people have a faster metabolism capacity and are thus called rapid metabolizers (RM). Others have an even faster metabolism and are called ultrarapid metabolizers (UM). In contrast, a significant proportion of the population metabolizes CYP2C19 substrates slowly. Those people with an impaired CYP2C19 function are known as poor metabolizers (PM). Finally, there is an intermediate phenotype, which reflects a distinctly

reduced function of CYP2C19. People with this phenotype are called intermediate metabolizers (IM). The proportion of these five phenotypes varies between ethnic groups, indicating a genetic component in the variability of CYP2C19. Currently, more than thirty alleles have been identified and described by the Pharmacogene Variation (PharmVar) Consortium.¹²⁻¹⁴ Table 1 below shows the phenotypes predicted on the basis of the different diplotypes.

Table 1: Genotype-based phenotype prediction for CY2C19 and phenotype frequency in Europe according to the Clinical Pharmacogenetics Implementation Consortium (CPIC) classification.^{12,14}

Predicted phenotype	Phenotype frequency in Europe	Genotype	Examples of diplotypes
UM	4.64%	Two increased function alleles	*17/*17
RM	27.12%	One normal function allele with one increased function allele	*1/*17, *11/*17, *13/*17, *17/*38
NM	39.61%	Two normal function alleles	*1/*1, *1/*18, *11/*38, *15/*28
IM	26.11%	One non-function allele with one increased function allele or one normal function allele	*1/*2, *1/*3, *2/*11, *4/*38
PM	2.39%	Two non-functional alleles	*2/*2, *3/*3, *7/*37, *22/*37

CYP2C19 is also subject to variability due to environmental, physiological and pathological factors. Inhibition by many drugs has been reported (such as with fluvoxamine)^{15,16}, as well as induction (such as with rifampicin)¹⁷. Finally, CYP2C19 activity might also be influenced by pregnancy, oral contraceptives and gender.¹⁸⁻²⁰

2.4 Assessment of CYP2C19 activity

Two approaches can be used to assess CYP2C19 activity: genotyping and phenotyping methods. Genotyping is based on DNA analysis and polymorphisms detection.²¹ Its major drawback is the incapacity to measure the influence of the environmental factors on CYP2C19 activity. Moreover, some rare variants may not be screened and an allele may be erroneously categorized as functional.²²

To characterize real-time activity of these enzymes, phenotyping is the preferred approach as it takes into account simultaneously genetic, endogenous and environmental factors.²³ Phenotyping consists of the administration of a probe drug specifically metabolized by an

isoenzyme. Omeprazole (OPZ)²⁴⁻²⁶ and mephenytoin^{27,28} are the most common probes used to assess CYP2C19 activity. The assessment of different PK parameters of the probe drug and its metabolite, or the determination of the metabolic ratio (MR) of the probe drug and its metabolite enable to define an individual metabolic profile. Thus, it provides relevant information about *in vivo* enzymatic activities that may be applied in clinical practice. Phenotyping tests are either selective or mixed, also known as a 'cocktail' phenotyping method. Selective phenotyping involves the administration of one probe drug whereas mixed phenotyping allows the determination of the activity of multiple enzymes concurrently.²⁹ The "Geneva Cocktail" has been developed by the Clinical Pharmacology and Toxicology Department at Geneva University Hospitals, to simultaneously assess the activity of six CYP isoenzymes (i.e. caffeine (CYP1A2), bupropion (CYP2B6), flurbiprofen (CYP2C9), omeprazole (CYP2C19), dextromethorphan (CYP2D6) and midazolam (CYP3A)). This cocktail combines the use of low-dose probes and the dried blood spots (DBS) sampling technique.³⁰ However, the main disadvantage of phenotyping with probe drugs is the potentially invasive nature of the procedure using exogenous substances. Indeed, their intake may not be well received by patients and study subjects. In addition, there may still be some security issues when administrating medications (e.g. dosage errors) and it is also necessary to wait few hours before DBS sampling after the cocktail intake which may be clinically impractical. Furthermore, it can hardly be administered to vulnerable populations (i.e. pregnant women, children and the elderly).²²

Therefore, replacing the probe drugs used in routine phenotyping with endogenous biomarkers may be more acceptable to patients and study volunteers, avoid any delay before sampling and completely eliminate any risk associated with exogenous substances.²²

2.5 CYP450 endogenous biomarkers

The search for CYP450 biomarkers is on the rise and endogenous ones are already promising for certain isoforms. Regarding CYP3A, cortisol and its metabolite 6-beta-hydroxycortisol as well as cholesterol and 4-beta-hydroxycholesterol are commonly used as endogenous probes despite some drawbacks.^{31,32} Furthermore, it has been shown that CYP3A specifically catalyzes 1-beta-hydroxylation of deoxycholic acid³³, which has recently been investigated in our lab by Magliocco et al³⁴. 5-omega and omega-1-hydroxylated medium-chain acylcarnitines have also been identified as novel CYP3A biomarkers by Kim B. et al. using an untargeted metabolomics approach.³⁵ Concerning CYP1A2, the 6-hydroxymelatonin/ melatonin MR in urine is considered as a potential endogenous metric.²² Indeed, CYP1A2 is the major enzyme involved in the 6-hydroxylation of melatonin and was recently investigated in our department in a clinical study by Magliocco et al. However, the suitability of such potential endogenous biomarker has yet to be clarified.³⁶ For CYP2D6, many studies have been conducted and

several endogenous compounds could be used (e.g. codeine/morphine, 5-methoxytryptamine/serotonin). We most recently discovered and identified through untargeted metabolomics and NMR, solanidine and its metabolite 3,4-seco-solanidine-3,4-dioic acid.^{22,37,38}

2.6 CYP2C19 endogenous biomarkers

In contrast, CYP2C19 still lacks endogenous probes that could be used clinically. Arachidonic acid (AA) and its metabolites have been identified as potential endogenous biomarkers for CYP2C19.^{22,39,40}

Despite this interesting finding, clinical validation remains necessary and other CYP450s, in particular CYP2C8 and 2C9, are also responsible for AA metabolism, which would compromise the specificity of the endogenous probe and the discovery of novel endogenous biomarkers of CYP2C19 is needed.²²

2.7 Metabolomics

Metabolomics refers to the study of small molecules (<1500 Da) present in a biological sample (biofluid, cell, tissue, organ or organism). Liquid chromatography coupled to high resolution mass spectrometry (LC-HRMS) is the universal method to perform metabolomics analysis because of its sensitivity, selectivity, resolution, high throughput, mass accuracy and capacity to generate MS/MS spectra. Nuclear magnetic resonance (NMR) as well as gas-chromatography coupled to mass spectrometry (GC-MS) are also frequently used.⁴¹ All these methods are complementary to each other and enable to expand the diversity and number of metabolites detected.

Metabolomics is commonly used in biomarkers discovery to understand, for example, response to environmental influences, therapy or diseases.⁴² It combines the measure of the environment and genetics. Thus, the metabolome could be also seen as a high-resolution phenotype.⁴³

Untargeted metabolomics is thus seen as a “*qualitative or semiquantitative analysis of the largest possible number of metabolites from a diversity of chemical and biological classes contained in a biological specimen*”.⁴⁴ In this project, untargeted metabolomics analysis using LC-HRMS will be used on plasma, urinary and liver-derived extracellular vesicles samples in order to measure the impact of genetics and environmental modulation of CYP2C19 on the metabolome.

2.8 Primary objective

The primary objective of this study is to identify and validate an endogenous substrate and/or metabolite of CYP2C19 activity using untargeted metabolomics and semi-quantitative targeted analysis in healthy volunteers.

2.9 Secondary objective

- Determination of the chemical structure of the discovered metabolites with internal or external databases, LC-MS/MS fragmentation, reference standards or NMR.
- Correlation of the relative abundance (or absolute concentration if the molecule has been identified and is commercially available) in urine and/or plasma and/or liver-derived extracellular vesicles of the discovered metabolite with the phenotype (blood $MR_{OH-OPZ/OPZ}$).
- Evaluation of the expression levels of CYP2C19 cell-free RNA (cfRNA) from extracellular vesicles and correlation with genotype, phenotype (omeprazole) and modulation of CYP2C19 activity by administration of an inhibitor (fluvoxamine) and an inducer (rifampicin).
- To compare CYP2C19 metabolomic signature of liver-derived extracellular vesicles with that of plasma and urine.
- To compare CYP2C19 metabolomic signature of liver-derived extracellular vesicles with that of total extracellular vesicles.
- Establishment of a multivariate linear regression model to predict CYP2C19 phenotype.
- Validation of the results with recombinant enzymes and human hepatocytes genotyped for CYP2C19.

3. STUDY DESIGN

3.1 Overall description

The study will be an open-label study with a total of 40 healthy volunteers fulfilling inclusion/non-inclusion criteria, divided into 2 study groups: 10 healthy volunteers PMs and 30 NMs-RMs-UMs for CYP2C19 and participating in the three sessions:

- Session 1: urine and venous blood sampling. Determination of blood $MR_{OH-OPZ/OPZ}$ at baseline (no inhibitor administrated).
- Session 2: urine and venous blood sampling. Determination of blood $MR_{OH-OPZ/OPZ}$ after pre-treatment by fluvoxamine (strong inhibitor of CYP2C19).

- Session 3: urine and venous blood sampling. Determination of blood MR_{OH-OPZ/OPZ} after pre-treatment by rifampicin (strong inducer of CYP2C19).

Information:

At this step, the volunteer will have an interview with one of the co-investigators at the Clinical Pharmacology and Toxicology department and the study will be explained in detail. A sufficient time will be allowed before the inclusion session to guarantee sufficient time for reflection.

Inclusion:

Volunteers willing to participate and having signed the informed consent form (ICF) will undergo a clinical evaluation with a physician including liver and kidney tests, body mass index, genotyping (except if CYP2C19 genotype is already known) and a pregnancy test (women only). Women will be asked to use at least one physical contraceptive barrier (i.e. male or female condom, diaphragm, spermicide) throughout their study participation and 1 month after the end of the study, in addition of their hormonal contraception if applicable. In case of heavy menstrual bleeding, women will have to be recruited before or after their menstrual period to avoid the presence of blood in urine. In addition, all volunteers will be asked to avoid alcohol consumption on days of taking study drugs and 48 hours before day 0 of session 1. A volunteer code for the study will be assigned to each volunteer included in the study.

Only volunteers fulfilling the inclusion/non-inclusion criteria will be allocated to a study group.

Sessions course:

Each session includes urine collection over a full 24-hour period that will start in the morning of day 0 for session 1, day 10±4d for session 2 and day 26±4d for session 3. It will end in the morning of day 1 for session 1, day 11±4d for session 2 and day 27±4d for session 3. Since most of this part will be performed at home, subjects will be given precise instructions on how to perform it. The last urine stream for each session will be collected in the morning after an overnight fast. Urine will be collected into a 24-hour collection container. This will be stored in a cooler with ice packs and/or a refrigerator.

Immediately after the 24-hour urine collection, venous blood (6 x 6 ml) will be collected and one 10 mg tablet of omeprazole (Antrumups®) administrated. Women will only receive omeprazole after verifying that they are not pregnant (urine test). 2 hours after omeprazole intake, capillary blood sampling (DBS sampling) will be performed. Volunteers will then be free to leave the HUG. Breakfast will be served after capillary blood sampling.

No wash-out period is necessary between the first and second session as fluvoxamine treatment lasts one week, which is sufficient to eliminate omeprazole administered in the first session, as well as its metabolites. Indeed, omeprazole's half-life elimination is generally less than 1 hour, and does not exceed 3 hours in PMs healthy subjects^{45,46}. However, a minimum of six days is necessary between session 2 and session 3. This time gap is required because of the half-life elimination of fluvoxamine being 19,5 hours on average after multiple intakes⁴⁷⁻⁴⁹.

Concerning the second session, participants will be instructed (orally and through reception of an instruction card) to take one 50 mg tablet of fluvoxamine (Floxyfral® junior) every morning for one week (7 doses in total) with the breakfast. If the third visit (session 2) happens exactly 7 days after the second visit (session 1), the drug must be taken during the lunch of session 1 (day 1) in order to have a total of 7 doses of fluvoxamine administrated. Otherwise, the treatment must start one week before the third visit (session 2) and the last dose must be taken 2 hours before omeprazole intake during the day 1 of session 2.

Concerning the third session, participants will also be instructed to take two 300 mg tablets of rifampicin (Rimactan®) every evening for 10 days (10 doses in total) before the fourth visit. This regimen will begin at least 6 days after the third visit (session 2) and the last rifampicin intake will be done at the evening preceding the fourth visit (session 3).

Volunteers will be asked to back empty blisters of the drugs that they took home in order to verify compliance.

The total study duration will not exceed 32 days. Therefore, the first dose of fluvoxamine and rifampicin must be taken, at the latest, 9 days and 21 days after day 1 of session 1, respectively (see study design page 13).

The order of sessions is purposely not randomized due to unnecessity. Indeed, as it is solely a PK study performed on paired samples, there are no possible biases requiring randomization.

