6.1 Urine collection

At each session, urine will be collected for 24 hours before omeprazole intake. The total urinary volume will be recorded, aliquoted and stored at -80°C until analysis. These samples will serve for the targeted and untargeted metabolomics analysis that will be carried out by the Laboratory of Forensic Toxicology and Chemistry at the University Centre of Legal Medicine and the Laboratory of Clinical Pharmacology and Toxicology of Geneva University.

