8. QUALITY CONTROL AND ASSURANCE

8.1 Data handling and record keeping/archiving

8.1.1 eCRF

The electronic Case Report Form (eCRF) is an investigator file, written for each study subject, which contains data necessary to the progress and the analysis of the study, including safety data.

In this study, the following data will be entered in the eCRF using the browser-based software REDcap :

- Review of inclusion and non-inclusion criteria (check boxes) *
- Demography: gender*, age*
- Concomitant medication(s)*
- weight*, size* and BMI*
- CYP2C19 genotype and phenotype
- For women: date of last menstrual cycle, contraception methods and pregnancy test result at each visit*
- Time of drug intakes*
- Time of venous and capillary blood samplings*
- Time of urine collections*
- SAE resulting in death and SUSARs*

All items followed by an asterisk will be entered directly in the eCRF and will be considered source documents.

Each page will include the subject's and visit's number as well as all the modifications dated and signed by the investigator.

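### The menstrual rule times recruitment, and only for heavy bleeding, so none of the three 24-hour urine collections is strictly kept free of blood

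*Protocol*

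**What the plan says.** Section 3.1, under Inclusion, holds the only menstrual rule in the text. It applies where bleeding is heavy: "women will have to be recruited before or after their menstrual period to avoid the presence of blood in urine". The stated purpose is to keep blood out of the urine.

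The same section, under Sessions course, states: "Each session includes urine collection over a full 24-hour period". The collections "start in the morning of day 0 for session 1, day 10±4d for session 2 and day 26±4d for session 3". Rifampicin starts no sooner than 6 days after session 2 and is taken on 10 evenings, the last one on the eve of session 3.

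Section 6.1 gives the use of the urine: "These samples will serve for the targeted and untargeted metabolomics analysis". Section 3.2 makes urine one of three matrices for the primary endpoint. It qualifies a feature as a biomarker on a fold-change of at least 1.5 or at most 0.67, and that sentence sets no p-value condition.

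The eCRF list in section 8.1.1 includes: "For women: date of last menstrual cycle, contraception methods and pregnancy test result at each visit". No section attaches a scheduling, postponement or exclusion rule to that date.

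**The concern.** The rule acts at the wrong point. Its aim concerns the urine samples, but it governs when a woman is recruited, and recruitment is not tied to day 0: the inclusion visit precedes session 1 by an unstated interval. The three collections then span about one menstrual cycle, so a start outside one period does not keep the later collections outside the next. Women whose bleeding is not heavy are not covered at all.

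The session comparison is within person. Blood in one session's urine and not in another's adds ions of blood origin to one side of that person's ratio. This raises the variance of the paired differences, and it can push the average fold-change of an ion that is scarce in clean urine past the 1.5 threshold.

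**Working it through.** The Protocol gives no figure on this point, so there is none to reproduce. The check counts start days.

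**Inputs from the Protocol (section 3.1).** Collections start on days 0, 10 and 26 and run from morning to morning, so each touches two calendar days. Windows are ±4 days for sessions 2 and 3. The minimum gap between visits 3 and 4 is 6 + 10 = 16 days.

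**Assumptions (not in the Protocol).** Regular cycle of L = 28 days, bleeding on cycle days 1 to B = 5, and cycle phase at day 0 uniform.

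**Overlap on nominal days.** Let c be the cycle day on which the session 1 collection starts. A collection overlaps bleeding if either of its two days falls on cycle days 1 to 5, that is, if it starts on cycle day 28 or 1 to 5.
- Session 1 with no effective rule: 6 of 28 start days overlap, 6/28 = 21%.
- Session 1 clear: c = 6 to 27, which is 22 start days.
- Session 2 overlaps when c + 10 lies in 28 to 33, so c = 18 to 23: 6/22 = 27%.
- Session 3 overlaps when c + 26 lies in 28 to 33, so c = 2 to 7, of which 6 and 7 are among the clear starts: 2/22 = 9%.
- Either: 8/22 = 36%.

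**Sensitivity.**
- Cycles of 26, 28 and 30 days with periods of 4, 5 and 6 days give 24% (26 and 4) to 48% (30 and 6).
- Counting one calendar day per collection at L = 28, B = 5 gives 7/23 = 30%.
- In a 26-day cycle only session 2 is affected.

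**Can the existing windows avoid it?** Session 2 may start at c + 6 to c + 14 and session 3 at c + 22 to c + 30, at least 16 days apart. Examples at L = 28, B = 5:
- c = 6: session 2 at +10 (cycle day 16), session 3 at +28 (34 − 28 = cycle day 6); both clear.
- c = 20: session 2 at +14 (34 − 28 = cycle day 6), session 3 at +30 (50 − 28 = cycle day 22); both clear, gap 16.

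A full search finds a clear schedule for every clear start day in all nine settings above. Among the settings tried more widely (24 to 35-day cycles, 4 to 7-day periods), the only failure was a 24-day cycle with 7 days of bleeding, where 6 of 16 start days (38%) have no clear schedule.

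**What it can do to the contrasts.** For illustration, take 15 naturally cycling women among the 30 NM-RM-UM volunteers: 15 × 0.27 ≈ 4 affected at session 2 and 15 × 0.09 ≈ 1 at session 3.
- *Fold-change.* If an ion rises F-fold in 4 of 30 and is unchanged in the rest, the mean ratio is (26 + 4F)/30. It reaches 1.5 at F = (45 − 26)/4 = 4.75. On a geometric mean it needs F = 1.5^(30/4) ≈ 21.
- *Significance.* If k of 30 pairs shift equally on the log scale and the rest do not move, t = √(29k/(30 − k)), whatever the size of the shift. For k = 4, t = √(116/26) = 2.11, p ≈ 0.043. For k = 8, t = √(232/22) = 3.25, p ≈ 0.003.
- *After FDR.* With the 5000 features expected in section 9.1 and an assumed 5% Benjamini-Hochberg level, p = 0.043 would be declared only if more than 4300 features had p-values that small. For p = 0.003 the number is about 290.

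**The case against.** The tempting stronger reading is that the rule clears session 1 and leaves sessions 2 and 3 open, so that contamination always falls on the drug side and mimics inhibition or induction. The text does not support this. Women without heavy bleeding are outside the rule, and recruitment is not day 0, so bleeding can also fall in session 1 (21% of start days above). The 27% and 9% are conditional on a clear session 1, which is an assumption and not something the rule secures.

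A reader might also take 36% as the share of participants, or of any one contrast. It is neither. Sessions 2 and 3 are each compared with session 1, so the shares per contrast are 27% and 9%, and only of naturally cycling women. Men are eligible, the age range runs to 65, hormonal contraception is expected, and the number of women is not fixed.

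Later steps also filter artefacts. Session contrasts carry an FDR adjustment (section 9.2), which about 4 affected pairs in 30 would be unlikely to pass on their own. Candidates are then compared between PMs and NMs-RMs-UMs at baseline, and blood-derived ions have no evident reason to follow CYP2C19 genotype. Correlation with the omeprazole ratio and in vitro validation come after that. These points stand, and they limit the harm.

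It can be said, too, that restricting the rule to heavy bleeding may be a deliberate judgement, and that staff can use the windows and the recorded date informally. That does not rescue the rule: even for heavy bleeding it times the wrong event, and nothing in the text directs staff to use the date. The flowchart figures are not available here and could not be checked.

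**Conclusion.** The point holds as a rule that misses its own stated aim. No session, including session 1, is strictly protected from menstrual blood in the urine. For a naturally cycling woman with a clear session 1, the chance of overlap on nominal days is about 27% at session 2 and 9% at session 3, 36% for either, with a range of 24% to 48%. These figures rest on assumed regular cycles and period lengths, and the share of all participants is lower by an amount the Protocol does not allow one to fix.

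The consequence is added noise in the paired urine contrasts and possible false hits where section 3.2 is applied as worded, on fold-change alone. It is not a systematic bias towards a drug effect, and many such artefacts would be removed by the FDR step and the baseline genotype comparison. Plasma and extracellular vesicle samples are not affected by this route. It should be corrected before sampling, because an analysis plan cannot reschedule a collection.

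**What to change.** Replace the recruitment rule in section 3.1 with a scheduling rule for every menstruating woman: place each of the three 24-hour collections outside expected bleeding, choosing day 0 accordingly and moving sessions 2 and 3 within the ±4-day windows and the 16-day minimum between visits 3 and 4 that the Protocol already sets. The last-period date already in the eCRF supplies the information.

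Add an eCRF item for bleeding during a collection. Leave such a urine sample out of the urine contrasts, or show a sensitivity analysis without it, and keep that session's plasma and extracellular vesicle samples.

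The cost is scheduling effort, one eCRF field, and possibly a few urine pairs fewer than the 30 planned in section 9.1. No visit, window, dose or number of doses changes. Irregular cycles, or a short cycle with long bleeding, will not always be avoidable, which is why the flag is needed as well.

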4.3 Non-inclusion criteria

- CYP2C19 IMs
- Participation in any other interventional clinical study within 3 months prior to inclusion
- Pregnant or breastfeeding woman
- Any pathologies, use of drugs or food that may affect CYP activity (based on the 'drug interactions and cytochromes P450 table published by the Service of Clinical Pharmacology and Toxicology, HUG⁵⁰ and on the investigator's knowledge)
- Medical history of liver transplantation
- Regular smokers of ≥ 10 cigarettes/day
- Alcohol intake 2 days prior to session 1 and during fluvoxamine and rifampicin intake
- Alteration of hepatic tests (ASAT, ALAT, GGT, bilirubin more than 3x normal)
- Renal failure (serum urea, serum creatinine and eGFR outside the norms)
- Medical history of chronic alcoholism or abuse of psychoactive drugs
- Sensitivity to any of the drugs used

- Psychiatric disorders
- Beck Score ≥ 10 (question related to suicide >0)
- Contact lens wearers

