4.5 Withdrawal criteria

Volunteers are free to withdraw from the study at any time without giving any explanation. If a volunteer withdraws from the study, a new volunteer will be included. The investigators may exclude a volunteer from the study for medical reasons or when eligibility criteria are not fulfilled anymore.

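### The alcohol restriction leaves day 0, the baseline 24-hour urine day, uncovered, whereas the collection days of sessions 2 and 3 are covered

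*Protocol*

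**What the plan says.** The alcohol rule appears in two forms.

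- Protocol 3.1 (Inclusion): "all volunteers will be asked to avoid alcohol consumption on days of taking study drugs and 48 hours before day 0 of session 1".
- Protocol 4.3, as a non-inclusion criterion: "Alcohol intake 2 days prior to session 1 and during fluvoxamine and rifampicin intake". The French synopsis (selection criteria) has the same content.

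Section 3.1 (Sessions course) fixes the sampling times. The 24-hour urine collections "start in the morning of day 0 for session 1, day 10±4d for session 2 and day 26±4d for session 3". On their end it says: "It will end in the morning of day 1 for session 1, day 11±4d for session 2 and day 27±4d for session 3". Blood and the probe drug follow: "Immediately after the 24-hour urine collection, venous blood (6 x 6 ml) will be collected and one 10 mg tablet of omeprazole".

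For fluvoxamine, outside the special case of a visit exactly seven days after session 1, "the treatment must start one week before the third visit (session 2) and the last dose must be taken 2 hours before omeprazole intake". Rifampicin is taken "every evening for 10 days (10 doses in total) before the fourth visit", the last dose on the evening before the visit.

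Section 3.1 also fixes the order of sessions, on the ground that no bias could call for randomisation. Section 4.5 adds: "The investigators may exclude a volunteer from the study for medical reasons or when eligibility criteria are not fulfilled anymore".

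**The concern.** The 48-hour clause comes before any study drug, so its likely purpose is to standardise the baseline sample. As worded, it stops at the moment that sample begins. The other clause follows drug days, and day 0 is not one.

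Session 1 is the reference for both the fluvoxamine and the rifampicin contrast, and it supplies the samples for the baseline genotype comparison. Ions that come from a drink, or from recent drinking, could be higher at session 1 than at either later session. Such ions would show a fold-change below 1 that has nothing to do with CYP2C19. Because all volunteers go through the sessions in the same order, nothing in the design balances this. The eCRF list in section 8.1.1 has check boxes for the eligibility criteria but no item on alcohol intake by session, so the effect could not be examined afterwards.

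**Working it through.** **1. The plan's own figure.** Section 9.1 gives 30 volunteers for a two-sided paired t-test with effect size 1.156, 80% power and alpha = 0.05/5000 = 0.00001. The noncentral t distribution gives n = 30 with power 0.804, so the figure reproduces. The present point does not depend on it.

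**2. Is day 0 covered?**

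| Collection | Days | Study drug on the day collection starts | Covered by 3.1? |
|---|---|---|---|
| Session 1 | 0 to 1 | none; omeprazole follows on day 1 | no |
| Session 2 (nominal) | 10 to 11 | fluvoxamine | yes |
| Session 3 (nominal) | 26 to 27 | rifampicin | yes |

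The 48 hours before day 0 are days −2 and −1. Baseline plasma, drawn on the morning of day 1, also follows the unrestricted day.

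The wording in 4.3 counts back from session 1. If that means the day 1 visit, the two days are −1 and 0, and day 0 is covered. If it means the session as 3.1 uses the term, with day 0 as its first day, the two days are −2 and −1, and day 0 is not covered. The two sections also differ on drug days: 3.1 covers every study drug, while 4.3 names only fluvoxamine and rifampicin.

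**3. Required alcohol-free days before each urine collection starts (nominal calendar).**

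- Session 1: days −2 and −1 = 2 days.
- Session 2: visit on day 11, seven doses on days 5 to 11, urine from day 10; days 5 to 9 = 5 days.
- Session 3: visit on day 27, ten evening doses on days 17 to 26, urine from day 26; days 17 to 25 = 9 days.

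Moving the visits by −4 or +4 days leaves 5 and 9 unchanged. With session 2 on day 8 and a first dose at lunch on day 1, the session 2 count is 6 (days 1 to 6).

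**4. How large could the effect be?** The protocol gives no input for this, so every value here is an assumption. Let a share f of volunteers have an ion at r times its alcohol-free level at session 1 and at its usual level later. Taking fold-change as the ratio of group means:

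later session / session 1 = 1 / (1 + f(r − 1))

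This is at or below 0.67 when r ≥ 1 + (1/0.67 − 1)/f = 1 + 0.4925/f:

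- f = 10%: r ≥ 5.9
- f = 20%: r ≥ 3.5
- f = 30%: r ≥ 2.6
- f = 50%: r ≥ 2.0

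A simulation (2,000 runs per setting, n = 30, r = 3, log SD 0.3 per measurement, paired t-test on logs) gives the chance that such an ion passes both a fold-change of ≤0.67 and a p-value limit. The limit p < 0.001 is an assumed stand-in for a false discovery rate cut-off (section 9.2). The limit 0.00001 is the level in section 9.1.

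| f | with p < 0.001 | with p < 0.00001 |
|---|---|---|
| 20% | 5% | 0.2% |
| 30% | 18% | 0.9% |
| 50% | 74% | 21% |
| 70% | 99% | 80% |

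**The case against.** Several points on the other side carry weight.

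- **Later filters.** A reader might infer that an alcohol-related ion could end up as the final CYP2C19 biomarker. The documents do not support going that far. Compounds found in the session contrasts go on to a baseline comparison of poor metabolisers with the other group, and nothing in the protocol ties drinking to genotype. Structure identification, correlation with the omeprazole ratio, and work with recombinant enzymes and hepatocytes follow.
- **Direction.** Sections 5.1.2 and 5.1.3 expect CYP2C19 metabolites to fall under fluvoxamine and rise under rifampicin. An ion that falls in both contrasts does not fit. This stands as an expectation only: section 3.2 sets no rule on direction.
- **Who is affected.** A reader might infer that every drinker shifts both contrasts. That is not shown. A drinker who abstains on day 0 differs only by 2 against 5 or 9 dry days, and nothing in the protocol shows an alcohol-related ion lasting beyond 48 hours.
- **Material not shown.** The overnight fast covers the end of the collection. The flowchart is not available, and the home-collection instructions could add a restriction.
- **Eligibility.** Sections 4.3 and 4.5 together might be read to mean that one drink during a drug course ends participation. Section 4.5 only permits exclusion, so that reading is too strong. What remains is that an on-study restriction sits in a list of non-inclusion criteria.

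These points reduce the consequence. They do not close the gap in 3.1, nor its conflict with one reading of 4.3.

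**Conclusion.** The gap is real on the text: the rule in section 3.1 does not cover the baseline collection day, and it does cover the corresponding days of the two later sessions. In a fixed-order paired comparison screened on fold-change, this treats the comparator session differently for no stated reason. The likely harm is extra false candidates and noise in the session screen.

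The size cannot be fixed from the protocol. It is small if few volunteers drink on day 0 and substantial only if about half or more have an affected ion, under the assumed threefold rise and log SD of 0.3.

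The unequal abstinence of 2, 5 and 9 days might suggest a nine-day run-in before baseline. That would leave session 2 at 5 days, so it would not equalise the sessions, and the documents give no sign that so long a period is needed. It is enough to close day 0 and record intake.

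**What to change.** 1. In section 3.1, let the pre-baseline restriction run without a break from 48 hours before day 0 through the blood sampling on day 1.
2. Reconcile section 4.3 and the synopsis with that wording: the day from which the two days are counted, which study drugs are meant, and the listing of an on-study restriction as a non-inclusion criterion, read together with section 4.5. How a volunteer who drinks during a drug course is handled is for the sponsor to settle.
3. Add alcohol intake before each session to the eCRF list in section 8.1.1, so that the remaining difference in abstinence (2, 5 and 9 days) can be examined.

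The cost is one more day without alcohol per volunteer and one eCRF item. Sample size, visits and procedures do not change.
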